#### *Additional analyses testing exploratory hypotheses*

1. To test if demographic and baseline mental health characteristics predict one's willingness to choose a certain kind of content, researchers will conduct a separate multiple logistic regression for each kind of content one can choose in the content selection portion of the *blu surfer* program. Researchers define a "kind" of content as a topic (eg, emotional support, motivation, personal experience) or format (eg, video, image, article, activity). As demographic predictors, researchers will include age, gender, ethnicity, country, education level, employment status, socio-economic status, and having received professional mental health support in the past. As baseline mental health predictors, researchers will include distress, self-efficacy, hopelessness, meaning and purpose in life, adaptive actions and thought, and loneliness.
2. To test if the kinds of content one chooses predict change in distress over 8 weeks, researchers will conduct an MLM regression with each kind (defined as in the above analysis) as a binary predictor, study timepoint as another predictor, and the interaction between selected kind and timepoint as predictors, as well as a participant identifier as a random intercept.
3. To test how many pieces of content one adds when they pull content from an annotated library vs when they find it independently online, researchers will conduct a t-test of numbers of content added to one's guide across the "blu surfer" and "online help seeking as usual" conditions.

4. To test if participants are more satisfied in the *blu surfer* condition than the *online help seeking as usual* condition, researchers will conduct a t-test comparing mean satisfaction across those conditions.
5. To test if participants are more likely to view their mental health resource guide when they choose content from a curated library than when they select it all on their own, researchers will conduct a t-test comparing the mean number of times participants viewed their guide across the *blu surfer* and *online help-seeking as usual* conditions at 8 weeks after creating the guide.
6. To evaluate how age moderates change in distress over 8 weeks among participants completing popular online content interventions, researchers will conduct a mixed effects model with distress as the outcome, age, timepoint, and their interaction as predictors, and a participant identifier as a random intercept.
7. To compare the frequency of insight experiences across the *blu-surfer* and *online help-seeking as usual* conditions, researchers will conduct a Chi-squared test.
8. To test how having an insight experience moderates the intervention's impact on change in distress over 8 weeks, researchers will run a mixed effects model with distress as the outcome, insight experience, measurement time point, and their interaction as predictors, and a participant identifier nested within experimental condition as a random intercept.
9. To test how baseline self-efficacy moderates the impact of the intervention on change in distress over 8 weeks, researchers will run a mixed effects model with distress as the outcome, baseline self-efficacy, measurement time point, and their interaction as predictors, and a participant identifier nested within experimental condition as a random intercept.
10. Researchers will test how engagement predicts improvement in distress at 8 weeks in two ways. First, researchers will run a mixed effects model with distress as the outcome, number of resources viewed from the list at week 8, measurement time point, and their interaction as predictors, and a participant identifier nested within experimental condition as a random intercept. Second, researchers will run a mixed effects model with distress as the outcome, number of pieces of content added to one's list, measurement time point, and their interaction as predictors, and a participant identifier

nested within experimental condition as a random intercept. These analyses will be limited to participants in the two popular online content conditions.

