#### *Additional analyses*

1. Duplicate the main analysis with the subset of participants who did not meet criteria for struggling with distress and thereby participated in the study without being compensated.
2. Duplicate the main analysis comparing the change in distress from baseline to week 4 follow-up rather than to week 8.
3. Duplicate the main analysis with the subset of participants who completed the week 8 follow-up.
4. Duplicate the main analysis but with the following covariates included in the mixed-effects model: gender (multiple choice), age (continuous), ethnicity (categorical), sexual orientation (categorical), education level (categorical), socioeconomic status (continuous), and if participants completed the study on a computer, tablet, or phone.
5. Use a one-way ANOVA to test between-group differences in distress at 8-week follow-up. If the omnibus ANOVA produces a significant F-score, researchers will conduct two planned contrasts to compare the experimental condition to each other condition, and will

compute Cohen's ds of these comparisons. Researchers will run the same ANOVA on the 4-week follow-up data and at post-intervention for outcomes collected then. Researchers will also conduct these ANOVAs on secondary outcomes.

6. Calculate Cohen's d effect sizes reflecting within-group intervention effects on distress for each condition from baseline to 4-week and 8-week follow-ups.
7. Run four logistic regression models with dropout as the outcome baseline measures as predictors to determine if they predict which participants drop out either before completing the intervention, before the post-intervention questions, or before the 4- and 8-week follow-ups.
8. Duplicate the main analysis including data from suspected bots/scammers.

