#### *Additional analyses testing exploratory hypotheses*

1. To test if demographic and baseline mental health characteristics predict one's willingness to choose a certain kind of content, researchers will conduct a separate multiple logistic regression for each kind of content one can choose in the content selection portion of the *lonely blu surfer* program. Researchers define a "kind" of content as a topic (eg, emotional support, motivation, personal experience) or format (eg, video, image, article, activity). As demographic predictors, researchers will include age, gender, ethnicity, country, education level, employment status, socio-economic status, and having received professional mental health support. As baseline mental health predictors,

researchers will include loneliness, distress, self-efficacy, hopelessness, meaning and purpose in life, and adaptive actions and thought.

2. To test if the kinds of content one chooses predict change in loneliness, researchers will conduct an MLM regression with each kind (defined as in the above analysis) as a binary predictor, study timepoint as another predictor, and the interaction between each kind and timepoint as predictors, as well as a participant identifier as a random intercept. This analysis will be limited to participants in the popular online content condition.
3. To evaluate how age moderates change in loneliness among participants in popular online content interventions across 8 weeks, researchers will conduct a mixed effects model with loneliness as the outcome, age, timepoint, and their interaction as predictors, and a participant identifier as a random intercept.
4. To compare the frequency of insight experiences across the popular online content (*lonely blu surfer*) and researcher-created content (*overcoming loneliness*) conditions, researchers will conduct a Chi-squared test.
5. To test how having an insight experience moderates the impact of the intervention on change in loneliness across 8 weeks, researchers will run a mixed effects model with loneliness as the outcome, insight experience, measurement time point, and their interaction as predictors, and a participant identifier nested within experimental condition as a random intercept.

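### The content-choice regressions in Studies 2 and 3 use plain logistic models with sparse categorical predictors and no safeguard, so separation is likely, and nearly certain if country is entered uncollapsed in a small to moderate arm

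*Combined protocol and SAP*

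**What the plan says.** In Study 2, item 1 of the additional analyses testing exploratory hypotheses states that "researchers will conduct a separate multiple logistic regression for each kind of content one can choose" within the Blu Surfer program. A kind is defined "as a topic (eg, emotional support, motivation, personal experience) or format (eg, video, image, article, activity"; the list is given by example only, so the number of models is open.

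Each model has 14 predictors. Eight are demographic: "As demographic predictors, researchers will include age, gender, ethnicity, country, education level, employment status, socio-economic status", and prior professional mental health support. Six are baseline scores: "researchers will include distress, self-efficacy, hopelessness, meaning and purpose in life, adaptive actions and thought, and loneliness". Study 3, item 1 under the same heading, sets out the same model for the Lonely Blu Surfer program.

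The Materials sections place the content library in one of three conditions, so the outcome exists in that arm only. Recruitment in both studies is online and in English, with no country limit stated.

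Some of the coding can be read from the covariate list under Additional analyses: "gender (multiple choice), age (continuous), ethnicity (categorical), sexual orientation (categorical), education level (categorical), socioeconomic status (continuous". Country and employment status are coded nowhere in the available text. Neither item gives a collapsing rule, a minimum category size, a penalised or exact alternative, or a rule for a model that fails to converge.

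**The concern.** In maximum-likelihood logistic regression, a category in which everyone or no one chose the content has no finite coefficient. Software typically reports a very large estimate with a huge standard error, and the Wald p-value carries no information. An open online sample may well include countries represented by one or two people, and gender, ethnicity, education and employment can also have thin categories.

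There are two consequences. The separated categories give no usable result. The large number of parameters relative to events also pushes the remaining odds ratios away from the null. Both are repeated for every topic and format, and each test is read at the 0.05 level. Without a rule set in advance, categories would probably be merged after a fit fails, with the outcomes already visible.

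**Working it through.** The plan states no arm size, country mix or selection rate for these models, so there is no planned figure to reproduce. Everything below rests on stated assumptions.

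**1. A single category.** A category of m people, each choosing the content with probability p, is all-yes or all-no with probability p^m + (1−p)^m.

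| m | p = 0.5 | p = 0.1 |
|---|---|---|
| 1 | 1.00 | 1.00 |
| 2 | 0.50 | 0.82 |
| 5 | 0.06 | 0.59 |
| 10 | 0.002 | 0.35 |

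One person alone in a country therefore guarantees separation, whatever the selection rate.

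**2. Country alone, by hand.** Assume 30% of the arm comes from 15 non-home countries of equal size, so the mean per country is λ = 0.30n/15: 2 people at n = 100 and 6 at n = 300. Treating counts as Poisson, the chance that a given country is present and separated is q = exp(−λ(1−p)) + exp(−λp) − 2exp(−λ). The chance of at least one is 1 − (1−q)^15.
- n = 100, p = 0.5: q = 0.368 + 0.368 − 0.271 = 0.465; result above 0.999.
- n = 300, p = 0.2: q = 0.008 + 0.301 − 0.005 = 0.304; result 0.996.
- n = 300, p = 0.5: q = 0.050 + 0.050 − 0.005 = 0.095; result 0.77.

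Equal country sizes are a favourable case. Uneven sizes leave more countries with one or two people.

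**3. The full model, by simulation.** Each cell had 200 data sets, with separation checked by linear programming. Assumed inputs were 8 continuous predictors (age, socio-economic status, six scores), 1 binary predictor, gender with 5 levels, ethnicity 7, education 6 and employment 6, rare levels at 2–5%, and selection rates of 0.2 or 0.5. With 15 non-home countries the parameter count, without the intercept, is 9 + (4 + 6 + 5 + 5) + 15 = 44 when every level is observed.

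Probability of any separation:

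| Arm size | 15 non-home countries | 5 non-home countries | Binary country, other factors at full levels |
|---|---|---|---|
| 100 | 1.00 | 1.00 | 0.96–1.00 |
| 200 | 0.995–1.00 | 0.79–0.99 | 0.71–0.97 |
| 300 | 1.00 | 0.47–0.94 | 0.33–0.86 |
| 500 | 0.875–1.00 | 0.08–0.61 | 0.04–0.43 |

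Events per parameter with 15 countries were 0.5–1.5 at n = 100 and 2.3–6.0 at n = 500.

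**4. Effect on a predictor that is not separated.** The true log odds ratio was 0.40, with 15 non-home countries and a plain fit.

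| Arm size | Median estimate | Coverage of 95% interval |
|---|---|---|
| 100 | 0.67 | 0.85 |
| 200 | 0.50 | 0.925 |
| 300 | 0.43 | 0.90 |
| 500 | 0.44 | 0.93 |

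At least one coefficient had a standard error above 50 in 93–100% of these fits. A further simulation with other assumed shares gave 0.64–0.83 at n = 100 and 0.47–0.52 at n = 200–300.

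**5. The remedy.** With Firth penalisation, country in three groups and levels under 10 people merged (n = 100, 150 and 300; 150 data sets per cell), every fit converged. The median estimate was 0.36–0.42 for the true 0.40, and no coefficient reached 5. Parameters fell from about 40–43 to 22–27.

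**The case against.** A reader might infer that these models are bound to fail as written and that their odds ratios are unusable in general. The documents do not support either reading.

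- **Unknown inputs.** The plan names variables without saying how country or employment will be coded. The available text gives no arm size, and since it omits some pages, one may be stated there. Across the codings and arm sizes in the table, separation ranges from 0.04 to 1.00. The low end needs a two-group country variable and 500 people.
- **Arm size may be larger.** The distress and loneliness criteria restrict the main analyses. Item 1 carries no such restriction, and people below the threshold may take part. The university subject pool could also concentrate the country mix.
- **Damage is partial.** Separation removes the affected categories. Age, socio-economic status and the six scores stay estimable, with little bias at 500. Hypothesis 1 covers those predictors too.
- **Sensitivity to shares.** At n = 300 and a 30% selection rate, the chance that nobody in a category of share s is a chooser is about (1 − 0.3s)^300: 16% at a 2% share and 1% at 5%. No document gives the shares.
- **Other remedies exist.** Ordinary logistic regression with country dropped and the other factors made binary (13 parameters) showed no separation at n = 100–500.

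All five points stand as limits on the claim. None supplies the missing safeguard. The low separation figures come from grouping that the plan does not specify.

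**Conclusion.** The concern holds in conditional form. The plan prescribes plain logistic regression with sparse categorical predictors in one arm and no protection against separation. If country is entered by individual country, separation is nearly certain in arms of about 100 to 300 people, assuming about 15 non-home countries of which some are very small. Even with equal country sizes it is 0.77 or higher from country alone at n = 300. Grouping country alone does not remove the problem, because other thin categories can separate; how often depends strongly on arm size and category shares.

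The separated categories' odds ratios and Wald p-values are unusable. The remaining log odds ratios are inflated in small arms (0.40 becomes about 0.6–0.8 at 100 people and about 0.5 at 200), with little bias by 500. The issue is confined to exploratory hypothesis 1 in Studies 2 and 3. It is a worthwhile improvement and does not threaten the trials' conclusions.

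**What to change.** In item 1 of the additional analyses testing exploratory hypotheses, in both Study 2 and Study 3:

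- Fit each content-choice model by Firth-penalised logistic regression and report profile-likelihood intervals. The estimates stay finite under separation, so this does not depend on the unknown arm size.
- State how country and employment status are coded. Before looking at the outcome, group country (for example into at most three categories) and merge very small categories of any factor (for example those with fewer than about 10 people).

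The cost is one software option and a short grouping rule. Country-level detail is lost, and estimates are slightly shrunk.

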### *Exploratory hypotheses:*

1. Demographics and baseline mental health characteristics predict one's willingness to choose a certain kind of content.
2. The kinds of content one chooses predict change in distress between baseline and 8-week follow-up.
3. Participants add more pieces of content to their guide when provided an annotated library to choose from VS when they have to seek out their own content without a library.
4. Participants are more satisfied with their mental health resource guides after completing it when they choose content from an annotated library than when they choose it themselves.
5. Participants are more likely to view their mental health resource guide after 8 weeks when they choose content from a curated library than when they select it all on their own.
6. Younger participants will experience a greater reduction in distress after the popular

online content interventions than older participants at 8 weeks.

7. The annotated library condition (*blu surfer*) is more likely to lead to an insight experience than online help-seeking as usual.
8. Having an insight experience during an intervention is associated with greater improvement in distress at 8 weeks.
9. Higher baseline general self-efficacy is associated with greater improvement in distress at 8 weeks.
10. Engagement with the SSI predicts greater improvement in distress at 8 weeks.

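### The model linking self-chosen content kind to change in the outcome has no baseline covariate, so its kind-by-time term can reflect who chose the content (item 2 of the exploratory analyses, Studies 2 and 3)

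*Combined protocol and SAP*

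**What the plan says.** In Study 2, under Additional analyses testing exploratory hypotheses, item 2 states that "researchers will conduct an MLM regression with each kind (defined as in the above analysis) as a binary predictor, study timepoint as another predictor". Besides these, the model has just two further terms: kind by timepoint, and a random intercept per participant. Study 3 item 2 has the same form, with loneliness as the outcome, and is limited to the popular online content arm. Neither item names a baseline covariate.

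Hypothesis 1 in both studies reads: "Demographics and baseline mental health characteristics predict one's willingness to choose a certain kind of content". Item 1 tests it by logistic regression on demographics and baseline scores. In Study 2 these are given as: "As baseline mental health predictors, researchers will include distress, self-efficacy, hopelessness, meaning and purpose in life, adaptive actions and thought, and loneliness". Study 3 item 1 lists the same six scales.

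Other hypotheses link baseline characteristics to improvement. Age is named in Study 2 hypothesis 6 and Study 3 hypothesis 3. Baseline general self-efficacy is named in Study 2 hypothesis 9 and Study 3 hypothesis 6.

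**The concern.** Content kind is chosen by the participant, not randomised. By the plan's own hypotheses, age and self-efficacy may relate both to the choice and to the amount of improvement. Item 1 lists these variables and item 2 leaves them out. The baseline outcome has a double role: it is a predictor of choice in item 1 and the starting point of the change in item 2.

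The result is likely to be read as showing which online content helps people who are distressed or lonely. The Missing data handling sections apply p < 0.05 to all analyses, so a kind with no effect could be reported as helpful or harmful because of who picked it.

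**Working it through.** **Is the omission repaired elsewhere?** No. The covariate rule under Missing data handling is triggered by faulty randomisation, which does not concern a self-selected exposure. The covariate-adjusted model under Additional analyses (item 4 in both studies) duplicates the main analysis only, and lists demographics and device but no baseline mental health score.

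**Inputs.** The plan gives no sample size, SD, correlation or strength of choice for this analysis, so there is no stated figure to reproduce. Assumed: n = 200 in the analysis, outcome SD 1, equal correlation r = 0.5 or 0.7 between visits, about half choosing the kind, an odds ratio (OR) for choice of 1.5 or 2.0 per SD of whatever drives it, no true content effect, complete data, two-sided 5% test. From the plan: visits at baseline, 4 and 8 weeks, and a random-intercept model with kind by time.

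**Route A: a baseline variable related to both choice and change.** The spurious week-8 contrast is minus (extra improvement per SD of the variable) x (gap in that variable between choosers and non-choosers). An OR of 1.5 gives a gap of about 0.39 SD and an OR of 2.0 about 0.63 SD. Take self-efficacy, with an assumed 0.2 to 0.3 SD more improvement per SD:

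- 0.2 x 0.39 = 0.08 SD
- 0.3 x 0.63 = 0.19 SD

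In simulation (change-score regression standing in for the planned contrast) the bias is -0.08 to -0.19 SD, with 8% to 35% false positives. Entering self-efficacy as a predictor of change brings the rate to about 5%. This route needs no regression to the mean.

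**Route B: the baseline outcome itself.** If choice follows the observed baseline score, the spurious contrast is -(1 - r) x baseline gap. For r = 0.7 and OR 1.5: -0.3 x 0.388 = -0.116. For r = 0.5 and OR 2.0: -0.5 x 0.620 = -0.310. If choice follows only the stable level, the gap persists to week 8 and the planned contrast is unbiased. The baseline-adjusted model is then off by about +(1 - r) x gap, which makes a neutral kind look harmful. For r = 0.7 and OR 1.5: 0.3 x 0.324 = 0.097.

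Simulation, n = 200, 2,000 runs per row (estimates in SD units; FP = false-positive rate):

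| Choice follows | r | OR | Baseline gap | Planned estimate | Planned FP | Baseline-adjusted estimate | Baseline-adjusted FP |
|---|---|---|---|---|---|---|---|
| Observed score | 0.5 | 1.5 | 0.383 | -0.190 | 27.1% | 0.002 | 5.1% |
| Observed score | 0.5 | 2.0 | 0.620 | -0.311 | 60.9% | 0.000 | 4.5% |
| Observed score | 0.7 | 1.5 | 0.388 | -0.116 | 17.7% | 0.001 | 5.8% |
| Observed score | 0.7 | 2.0 | 0.626 | -0.188 | 39.4% | 0.000 | 5.0% |
| Stable level | 0.5 | 1.5 | 0.278 | 0.000 | 4.3% | 0.141 | 20.4% |
| Stable level | 0.5 | 2.0 | 0.443 | 0.001 | 5.1% | 0.234 | 46.8% |
| Stable level | 0.7 | 1.5 | 0.324 | -0.002 | 6.0% | 0.098 | 16.8% |
| Stable level | 0.7 | 2.0 | 0.528 | 0.001 | 4.3% | 0.171 | 38.0% |

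Coding time as a factor or as 1-2-3 makes almost no difference. With choice unrelated to the baseline score (OR 1.0), the planned contrast rejects in 4.4% to 5.1% of runs.

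**Would main effects be enough?** No. A baseline covariate does not vary over time within a person. With complete data, entering it as a main effect leaves the kind-by-time estimate unchanged. It has to enter with its own interaction with time.

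**The case against.** Hypothesis 2 says only that chosen kinds predict change, and it is labelled exploratory. The planned model estimates that unadjusted association, and no primary or secondary conclusion depends on it. This stands, and it limits the weight of the point. It does not remove it, because the plan itself names variables that could produce the association.

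A reader might infer that a kind favoured by more distressed people must show improvement through regression to the mean, and that baseline-adjusted analysis should replace the planned model. The documents do not support this. They do not say whether choice follows momentary or stable distress, and the last four rows of the table show the adjusted model failing where the planned one is sound.

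A reader might also infer that recruiting people with high PHQ-4 scores makes the bias worse. Regression to the mean from entry selection that affects choosers and non-choosers alike goes into the time effect; only a difference between them matters. The restriction to distressed participants is also stated for the main analyses only.

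Finally, a reader might extend the point to Study 2 items 8 and 10 (insight and engagement) or Study 3 item 5. They too lack baseline covariates, but hypothesis 1 concerns the choice of content, so the plan's own prediction does not reach them. One wording point remains. Study 2 item 8 is described as testing moderation of the intervention's impact, yet its fixed terms are "insight experience, measurement time point, and their interaction as predictors", with no term by condition. It can show only an association, which is what hypothesis 8 states.

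**Conclusion.** The point holds for item 2 in Studies 2 and 3. On the plan's own hypotheses, the kind-by-time term can show a content effect that reflects who chose the content, and nothing else in the plan corrects this. Confounding by variables such as age and self-efficacy does not depend on regression to the mean. The baseline-outcome route is conditional: under the assumed n, r and odds ratios, the planned contrast's false-positive rate lies anywhere from about 5% to about 60%, depending on what drives the choice. These figures show what is possible; they are not estimates for this trial. The point is worth correcting before analysis but touches only exploratory results.

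**What to change.** In item 2 of both studies:

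1. Keep the planned model.
2. Add a version with the item 1 baseline predictors, each with its interaction with time: the demographic variables and the mental health scores other than the outcome (so without distress in Study 2 and without loneliness in Study 3).
3. Also report a version that models the week-4 and week-8 scores with the baseline outcome as covariate.
4. State in advance that a kind will be called associated with improvement only if the versions agree, and that the result is an association.

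In Study 2 item 8, replace the moderation wording with association.

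The cost is SAP text and extra model terms. The predictors are already named in item 1, and the baseline scores are in Tables 3 and 5. The drawback is some loss of precision, because the analysis rests in practice on a single arm and item 1 includes several categorical variables. Requiring agreement between versions also makes it harder to report a real association.

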6. To test how baseline self-efficacy moderates the impact of the intervention on change in loneliness across 8 weeks, researchers will run a mixed effects model with loneliness as the outcome, baseline self-efficacy, measurement time point, and their interaction as predictors, and a participant identifier nested within experimental condition as a random intercept.

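### Study 2 item 9 and Study 3 item 6 promise a test of whether self-efficacy moderates the intervention's effect, but their model has no term that differs by arm and can answer only a prognostic question

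*Combined protocol and SAP*

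**What the plan says.** Under *Additional analyses testing exploratory hypotheses*, Study 2 item 9 opens "To test how baseline self-efficacy moderates the impact of the intervention on change in distress over 8 weeks" and Study 3 item 6 opens "To test how baseline self-efficacy moderates the impact of the intervention on change in loneliness across 8 weeks".

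The Study 2 model has "distress as the outcome, baseline self-efficacy, measurement time point, and their interaction as predictors", with "a participant identifier nested within experimental condition as a random intercept". Study 3 uses the same structure with loneliness as outcome. Neither item restricts the arms, so all three are pooled. The limit to the popular-content conditions at the end of Study 2's list belongs to item 10.

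The hypotheses behind these items are worded differently. Study 2 exploratory hypothesis 9 reads "Higher baseline general self-efficacy is associated with greater improvement in distress at 8 weeks", and Study 3 exploratory hypothesis 6 is its counterpart for loneliness. Study 1 fits the same kind of model for self-efficacy and describes it as a test of association with change.

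Elsewhere, the plan estimates an arm effect through time by condition (*Main analysis*, Studies 2 and 3). No section specifies a term for a baseline characteristic by time by condition. The 0.05 criterion applies to all analyses (*Missing data handling*, Studies 2 and 3).

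**The concern.** In this plan, the intervention's effect is the difference between arms in change over time. To say that self-efficacy moderates that effect is to say that the difference between arms varies with self-efficacy. The specified models cannot express this, because they give one self-efficacy slope to everyone.

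If the stated aim is carried into the report, a significant self-efficacy by time term could be presented as evidence about who benefits from a program when every arm shows the same gradient. A null term could equally be presented as evidence against moderation when the arms differ in opposite directions. The stake is a mislabelled exploratory claim.

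**Working it through.** The documents give no sample size, power or effect size for these analyses, so there is no figure to reproduce. The check is structural, with a simulation as illustration.

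**1. Terms present and terms needed**

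| Term | Study 2 item 9 / Study 3 item 6 | Needed for moderation of an arm effect |
|---|---|---|
| self-efficacy, time, self-efficacy × time | yes | yes |
| condition, time × condition, self-efficacy × condition | no | yes |
| self-efficacy × time × condition | no | yes (this is the test) |
| condition as a random-intercept level | yes | does not help |

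A random intercept shifts a group's level at all visits alike. It does not let change over time, or the dependence of change on self-efficacy, differ by arm. In one simulated dataset the self-efficacy by time estimate was -0.0985 (p = 0.0004) both with and without nesting the intercept in condition.

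**2. What the pooled coefficient estimates**

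Write the slope of baseline-to-week-8 change on self-efficacy in arm k as p + m_k, where p is common to all arms and m_k is specific to arm k. With three equal arms the two-way model estimates p + (m_1 + m_2 + m_3)/3.

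- Prognosis only, p = -0.2 and all m_k = 0: -0.2.
- Moderation in one arm only, p = 0 and m = (-0.6, 0, 0): -0.6/3 = -0.2, the same value.
- Moderation that cancels, p = 0 and m = (-0.4, +0.4, 0): 0.

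So the same coefficient can arise with no moderation or with strong moderation, and a zero coefficient does not exclude moderation.

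**3. Illustration by simulation**

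All inputs are assumptions: three equal arms, three visits with numeric time, no dropout, baseline SD 1, intraclass correlation 0.5, a standard-normal characteristic, two-sided 0.05 and 2,000 runs per cell. The comparison test is the three-way term on 2 df.

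| Truth | Per arm | Planned two-way significant | Three-way significant |
|---|---|---|---|
| Same 0.2 SD gradient in every arm, no moderation | 50 / 100 / 200 | 67% / 94% / 99.8% | 4.8% / 5.5% / 5.6% |
| Moderation -0.4, +0.4, 0 by arm | 50 / 100 / 200 | 6.8% / 6.4% / 6.6% | 94% / 99.9% / 100% |
| No gradient at all | 50 / 100 / 200 | 4.8% / 5.1% / 5.4% | 4.8% / 4.0% / 4.7% |

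**4. Closed-form cross-check of the first row**

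For a correlation r between self-efficacy and change in n people, power ≈ Φ(atanh(r) × √(n - 3) - 1.96). Take n = 300, so √297 = 17.23:

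- r = 0.20: 0.2027 × 17.23 = 3.49, power 0.94.
- r = 0.15: 0.1511 × 17.23 = 2.60, power 0.74.
- r = 0.10: 0.1003 × 17.23 = 1.73, power 0.41.

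**5. Precision cost of the three-way contrast**

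With n per arm and equal spread of self-efficacy, the variance of the pooled slope is proportional to 1/(3n). The variance of a difference between two arms' slopes is proportional to 1/n + 1/n = 2/n. The ratio is 6, so the standard error is about √6 = 2.45 times as large.

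**The case against.** The strongest reply is that the model is right and only two sentences are loose. The section exists to test the listed hypotheses. Those hypotheses are prognostic, and self-efficacy by time addresses them. This stands: rewording alone would make items 9 and 6 consistent with their hypotheses. It does not rescue the stated aim of testing moderation of the intervention's effect.

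Several stronger readings are tempting, and the documents do not support them.

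- *A reader might infer that the age analyses share the fault.* Study 2 item 6 reads "To evaluate how age moderates change in distress over 8 weeks among participants completing popular online content interventions" and fits a model "with distress as the outcome, age, timepoint, and their interaction as predictors"; Study 3 item 3 reads "To evaluate how age moderates change in loneliness among participants in popular online content interventions across 8 weeks". Both speak of moderating change, not the intervention's effect, and their hypotheses compare younger with older people within popular content. The models answer that. They cannot attribute an age gradient to popular content, but the items do not claim to.
- *A reader might take the word for completing in Study 2 item 6 as a completers-only set.* The protocol routinely uses that verb for undergoing an intervention, the Study 3 counterpart refers simply to participants in it, and no completer set is defined.
- *A reader might treat the 94% as a false-positive rate.* It is power to detect a gradient assumed to exist. Under the prognostic hypothesis it is a correct detection, and it misleads only if reported as moderation.
- *A reader might say the coefficient shows only who would improve anyway.* It mixes prognosis with arm-averaged effects and cannot separate them.
- *A reader might add that regression to the mean biases the result.* That depends on an assumed link between low self-efficacy and high baseline severity, and it would work against the hypothesis.

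The three-way term also has a limit. Blu Surfer against ABC compares two active programs, and Study 3's control is an active supportive program. If self-efficacy shaped benefit equally in both, the contrast would be zero. It measures differential moderation between the arms compared.

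**Conclusion.** The point holds for Study 2 item 9 and Study 3 item 6. Their stated aim is moderation of the intervention's effect, and their model cannot test it because no term lets the self-efficacy slope differ by arm. The model does answer the prognostic hypotheses it was written for. This conclusion follows from the listed terms and needs no assumption about sample size.

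The rejection rates show how far the two questions can diverge. They rest on assumed arm sizes, gradients and correlation structure with complete data, so they are illustrative. The analyses are exploratory, and the main time-by-condition results are untouched. The age analyses match their own hypotheses and are not at fault.

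**What to change.** 1. In Study 2 item 9 and Study 3 item 6, keep the two-way model for the existing hypotheses and describe it as a test of whether baseline self-efficacy is related to change, in line with Study 1.
2. For any claim of moderation, fit self-efficacy by time by condition with all lower-order terms in all randomised arms. Report the week-8 three-way contrasts of the experimental arm against each other arm, primary pair first. In Study 2 that is Blu Surfer against ABC, then against online help-seeking as usual. In Study 3 it is Lonely Blu Surfer against Sharing Feelings, then against Overcoming Loneliness. Describe each as differential moderation between the two arms compared.
3. Optionally, add the same three-way term with age in place of self-efficacy, using all arms, if an age gradient is to be attributed to popular content.

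No new data are needed, since self-efficacy is already measured at baseline (Tables 3 and 5). With three arms and numeric time, the moderation model adds four sets of two coefficients (condition, its two two-way interactions and the three-way term), eight in all. The main cost is precision: with standard errors about 2.45 times as large, under the equal-arm assumption above, these contrasts may be inconclusive and should be reported with confidence intervals.
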